12.4.2 Analysis of Secondary Endpoints

For **SH**, We will estimate a separate mixed-effects model for each of the four a-priori PVS ROIs. Models of PVS ROIs will include change from baseline to Week 5, Week 5 to 9 and models of behavioral activation (BADS scale) and depression severity (MADRS scale) and will include change from baseline to Week 3 to Week 5 and Week 5 to Week 9 as independent variables. Dependent variables will be depression severity at Weeks 5 and Week 9 for PVS ROI models and at Weeks 3, 5, and 9 for BADS model. We will include fixed effects for age, gender, antidepressant use, or any other variable that will be unbalanced between the groups. We will explore in all models the inclusion of higher order(s) of the time variable (e.g., quadratic, cubic, etc.) and choose the final model based on Bayesian Information Criterion (BIC).⁴⁷ We will control the overall Type I error

rate at 5% using Holm's stepdown procedure to adjust for four post-hoc multiple comparisons (four PVS ROIs) in **H1** and five comparisons (four PVS ROIs and BADS) in **SH**.

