1.2.3 Exploratory Objectives

Evaluate whether in “Engage & Connect” treated participants, change in rsFC of the PVS and behavioral activation (BADS) predicts subsequent reduction in depression severity (MADRS).

Investigate changes in social reward processing over the course of psychotherapy using a novel Social Incentive Delay (SID) fMRI task

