We will implement mixed-effects models using the *lme4* package in R.⁴⁶ For **H1, H2, and H3** we will include subject-specific random intercept and fixed effects for time-related parameter(s). For **SH**, We will estimate a separate mixed-effects model for each of the four a-priori PVS ROIs. Models of PVS ROIs will include change from baseline to Week 5, Week 5 to 9 and models of behavioral activation (BADS scale) and depression severity (MADRS scale) and will include change from baseline to Week 3 to Week 5 and Week 5 to Week 9 as independent variables. Dependent variables will be depression severity at Weeks 5 and Week 9 for PVS ROI models and at Weeks 3, 5, and 9 for BADS model. We will include fixed effects for age, gender, antidepressant use, or any other variable that will be unbalanced between the groups. We will explore in all models the inclusion of higher order(s) of the time variable (e.g., quadratic, cubic, etc.) and choose the final model based on Bayesian Information Criterion (BIC).⁴⁷ We will control the overall Type I error rate at 5% using Holm’s stepdown procedure to adjust for four post-hoc multiple comparisons (four PVS ROIs) in **H1** and five comparisons (four PVS ROIs and BADS) in **SH**.

SH. In “Engage & Connect” treated participants, change in: **SH1a.** rsFC of the PVS; and **SH1b.**

Behavioral activation (BADS) will predict subsequent reduction in depression severity (MADRS). These relationships will not be observed in the SRP treated group. Five mixed-effects models (as described above) will investigate whether change in the predictor is associated with subsequent change in depression severity (MADRS).

Power Analysis

Our primary outcome is change over 9 weeks of “Engage & Connect” in resting state functional connectivity (rsFC) of the Positive Valence System (PVS) (**H1**). Our secondary outcome measures are change in behavioral activation measured by the Behavioral Activation for Depression Scale (BADS) (**H2**); and depression severity, measured by the Montgomery-Asberg Depression Rating Scale (MADRS) (**H3**). Our secondary hypothesis (**SH**) investigates whether early change in the predictors (i.e. rsFC of the PVS and BADS change) predict subsequent change in depression severity (MADRS). We will measure rsFC at baseline, Week 5, and Week 9 and behavioral activation and depression severity at baseline, Week 3, Week 5, and Week 9.

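### The SH models set a MADRS level against predictor change ending at the same visit, so a concurrent association can be reported as prediction of later improvement

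*Combined protocol and SAP*

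**What the plan says.** Section 1.2.3 sets the aim of finding whether change in rsFC and BADS "predicts subsequent reduction in depression severity (MADRS"). Section 12.1 repeats this: early change in the predictors is to "predict subsequent change in depression severity (MADRS"), and it gives the purpose of the analysis as "Five mixed-effects models (as described above) will investigate whether change in the predictor is associated with subsequent change in depression severity (MADRS").

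Sections 12.1 and 12.4.2 then specify those models in the same words:

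- Predictors, ROI models: "Models of PVS ROIs will include change from baseline to Week 5, Week 5 to 9".
- Outcome, ROI models: "Dependent variables will be depression severity at Weeks 5 and Week 9 for PVS ROI models".
- Outcome, BADS model: MADRS "at Weeks 3, 5, and 9 for BADS model".
- Covariates: age, gender, antidepressant use, and anything else found unbalanced between the arms. MADRS at the start of an interval is not named.
- One sentence is not grammatical: "models of behavioral activation (BADS scale) and depression severity (MADRS scale) and will include change from baseline to Week 3", and it continues to the later intervals. It can mean the model linking BADS to MADRS, or it can mean that MADRS change is itself a regressor.

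No lag between predictor and outcome is stated. Under Section 6.1, MRI is done at baseline and Weeks 5 and 9, and MADRS and BADS at baseline and Weeks 3, 5 and 9. Section 6.1.3 provides no follow-up after Week 9.

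**The concern.** The hypothesis is about order in time: the predictor changes first and depression improves afterwards. The specified model does not isolate that, for two reasons.

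1. **Pairing.** The first ROI interval ends at Week 5 and the second at Week 9, and the outcomes are MADRS at Weeks 5 and 9. Taken in order, each predictor change is set against MADRS at the visit where that change ends. No ROI change is available before Week 5, and no MADRS is available after the Week 5 to 9 change.
2. **Level as outcome.** Even with a correct lag (ROI change to Week 5, then MADRS at Week 9), the Week 9 level contains baseline severity and all the MADRS change that took place alongside the predictor. Only the Week 5 to 9 part comes afterwards.

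At stake is the mechanism claim in Sections 3.1 and 12.1, that the therapy works by reconditioning the Positive Valence System. Section 12.4.2 also promises 5% Type I error control over the five SH tests. That control would not hold for a claim about subsequent change.

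**Working it through.** The plan gives no effect size, SD or power figure for SH, so there is no figure to reproduce.

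**Inputs from the documents.** 30 per arm (Section 1.1); attrition about 10% (Sections 4.1 and 7.12), so 30 × 0.9 = 27; Holm over five tests (Section 12.4.2), first step 0.05/5 = 0.01.

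**Assumptions, not in the documents.** MADRS SD 5 at baseline, SD of change 6 over Weeks 0 to 5 and 5 over Weeks 5 to 9, the three parts independent. The predictor correlates ρ with MADRS change in its own interval and has no relation to later change.

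**Step 1: lagged model, Week 9 level, no Week 5 MADRS.**

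MADRS9 = baseline + change(0–5) + change(5–9), so SD = √(25 + 36 + 25) = √86 = 9.27.

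Induced correlation with the predictor: r = ρ × 6/9.27 = 0.647ρ. By Fisher's transformation, z = atanh(|r|) × √(27 − 3).

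| ρ | r | z | Rejects at 5% | Rejects at 1% |
|---|---|---|---|---|
| 0 | 0 | 0 | 5% | 1% |
| -0.3 | -0.194 | 0.963 | 16% | 5% |
| -0.5 | -0.324 | 1.644 | 38% | 18% |

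Simulation under the same assumptions agrees (16% and 39% at the 5% level). If the Week 5 to 9 SD is 6, the factor is 6/√97 = 0.609 and the 5% rates become 15% and 34%.

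**Step 2: same data with the fix.** With Week 5 MADRS as covariate, the simulated rates are 4.7% and 4.9% at the 5% level and 0.9% and 0.8% at the 1% level. With the Week 5 to 9 change as outcome the 5% rate is also about 5%. With MADRS reliability of 0.8, the 1%-level rates are 4.5% and 14% (level alone), 1.2% and 1.7% (Week 5 adjusted), and 1.0% and 1.0% (change score).

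**Step 3: the listed intervals taken in order, without a lag.** This is a random-intercept model with time, two rows per participant, n = 27, baseline SD 5 and both interval-change SDs 6. A rejection counts as a false finding of subsequent change.

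| Model, 5% level | ρ = 0 | ρ = -0.3 | ρ = -0.5 |
|---|---|---|---|
| Intervals ending at the outcome visit | 5% | 28% | 66% |
| Same, plus start-of-interval MADRS, still no lag | 5% | 57% | 98% |
| Lagged, baseline MADRS only (one row) | 5% | 18% | 43% |
| Lagged, Week 5 MADRS (one row) | 5% | 5% | 5–6% |

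Both parts are needed. Baseline MADRS alone does not cure the problem, and start-of-interval MADRS without a lag makes it worse.

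**Step 4: a true later effect only.** For a lagged correlation of -0.3 or -0.5 and no concurrent one, power at 5% is 16% or 34% for the unlagged level model, against 33% or 76% for the lagged model with Week 5 MADRS.

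**Step 5: MADRS change as a regressor.** On this other reading of the unclear sentence, the false rate is about 5%, but a true later effect is found in only 9% or 16% of trials. That version does not test SH either.

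**Step 6: BADS.** A lag-paired, stacked random-intercept level model gives about 10% at the 5% level and 3.5% at 1% for ρ = -0.5. From 600 trials, the Monte Carlo SEs are √(0.10 × 0.90/600) = 1.2 points and √(0.035 × 0.965/600) = 0.75 points.

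**The case against.** - **The planned data can test SH.** This stands. A reader might infer that SH is untestable, but ROI change to Week 5 followed by MADRS from Week 5 to Week 9 uses visits already scheduled. The fault lies in the specification.
- **Inflation is conditional.** This stands. With no concurrent correlation the rate stays at 5%, so it is too strong to say that the models will credit concurrent change.
- **The 16% and 38% are not for the planned mixed model.** True. They come from a one-row lagged regression, chosen to show that the level outcome is a fault even when the lag is right. The two-row model in Step 3 is worse, but it takes the listed intervals in order. That is the plain reading, though the plan does not state it.
- **MADRS on both sides.** A reader might infer from the ungrammatical sentence that MADRS change is both outcome and regressor. The documents do not settle this. The count of five SH comparisons, four ROIs and BADS, favors reading the sentence as the BADS-to-MADRS model. For the same reason, it cannot be said with certainty that the BADS model contains no earlier MADRS.
- **Baseline MADRS could enter as an unbalanced variable.** Possible, but the trigger is imbalance between arms, and Step 3 shows that baseline MADRS alone is not enough.
- **SRP as a control.** Sections 3.1 and 12.1 expect no such relationship under SRP. A non-specific concurrent association would tend to appear there too, which is a partial safeguard. It does not establish order in time within the Engage & Connect arm.

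**Conclusion.** The concern holds in a limited form. The stated SH outcome is a level, the listed predictor intervals end at the outcome visits, and no start-of-interval MADRS is named for the ROI models. The models therefore do not match their stated purpose of testing subsequent change. Under the assumed SDs of 5, 6 and 5 and n = 27, a lagged Week 9 level model without Week 5 MADRS gives about 16% or 38% false positives at the 5% level for concurrent correlations of -0.3 or -0.5. The fix gives about 5%. The rates depend on SDs and correlations that the documents do not supply, and they are smaller for a stacked BADS model.

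A reader might also infer that the trial's main conclusion is at risk. It is not: the primary endpoint is H1, and H1 to H3 do not use these models. SH is exploratory in Section 1.2.3 and secondary in Sections 12.1 and 12.4.2. The problem should be corrected before analysis because SH carries the mechanism claim.

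**What to change.** In Sections 12.1 and 12.4.2:

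1. State the lagged pairs: ROI change baseline to Week 5 with MADRS change Week 5 to 9; BADS change baseline to Week 3 with MADRS change Week 3 to 5; BADS change Week 3 to 5 with MADRS change Week 5 to 9.
2. Use MADRS change over the later interval as outcome, or the later level with start-of-interval MADRS as a mandatory covariate. Name one as the main analysis and report the other as a sensitivity analysis.
3. Rewrite the unclear sentence so that BADS change is plainly the predictor and MADRS the outcome.
4. If same-interval associations are reported, label them concurrent.

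**Cost.** No new data are needed, since MADRS is already collected at baseline and Weeks 3, 5 and 9. The change is nevertheless more than wording. Each ROI model falls to one row per participant, so it becomes an ordinary regression: a random intercept cannot be estimated, and choosing higher-order time terms by BIC no longer applies. The Week 5 to 9 ROI change cannot serve as a predictor of later MADRS. The covariate form uses one degree of freedom per model.

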“Engage” reduces late-life depression and disability.^{23,24} Early increase in resting state functional connectivity (rsFC) in PVS structures during “Engage” predicts increase in behavioral activation.²⁵ Change in behavioral activation is followed by reduction of depressive symptoms.²⁶ In order to further streamline “Engage” and guide its personalization, we examined whether specific types of “reward exposure” have higher therapeutic value. Activities involving social interactions with significant others (but not solitary activities) predicted subsequent increase in behavioral activation and reduction of depression.²⁷ We have also documented that high perceived social support predicts early response to psychotherapy.²⁸ Exposure of socially isolated older adults to social rewards during “Engage” led to greater reductions of depression than a ‘care as usual’ condition.²⁹ The above findings underscore the therapeutic role of rewarding social interactions with significant others. Based on this work, we developed “Engage & Connect”, a streamlined version of “Engage”, whose principal intervention is exposure to meaningful, rewarding social activities with significant others. “Engage & Connect” aims to recondition PVS functions, increase behavioral activation, and lead to reduction of symptoms of depression.

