2.3 Rationale

The proposed study will be the first study to test target engagement of “Engage & Connect”, a social reward-focused intervention for mid- and late-life depression. “Engage & Connect” is innovative because: 1) It is directly informed by neurobiological research and designed to address dysfunction of PVS, a core component of depression; 2) It is based on data

demonstrating that exposure to social rewards has the highest probability to improve depressive symptoms; 3) It is streamlined so that it can potentially be used by community clinicians. The NIMH Strategies 3.1; 3.2 encourage the development of novel streamlined treatments informed by advances in neuroscience.

To our knowledge, the proposed study will be the first to examine neural processing of social rewards in mid- and late-life depression. It is based on computational modeling, which identified perceived social support as the strongest predictor of early response to psychotherapy and examines whether PVS changes by mid-treatment predict response of depression to “Engage & Connect”. Along with other PVS function measures, it uses a novel social reward fMRI paradigm to examine PVS change and its relationship to “Engage & Connect” response. Behavioral tasks and clinical scales across multiple units of analysis are quick, cost-effective, and easy to administer, making them feasible to use in future large-scale studies and as screening tools in clinical settings.

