6.1 Schedule of Assessments

Patient participants will be randomized to receive a 9-week course of either weekly Engage & Connect therapy or SRP, and research assessments will be conducted at baseline and weeks 3, 5, and 9.

| Week | Baseline | 1 | 2 | 3 | 4 | 5 | 6 | 7 | 8 | 9 |
|----------------------------|----------|---|---|---|---|---|---|---|---|---|
| Therapy Session | | x | x | x | x | x | x | x | x | x |
| Research Assessment | x | | | x | | x | | | | x |
| MRI Scans | x | | | | | x | | | | x |

Trained research assistants unaware of study hypotheses will collect weekly clinical and self-report ratings at each study time point.

| Instrument | Baseline | Week 1 | Week 3 | Week 5 | Week 9 |
|---|----------|--------|--------|--------|--------|
| Demographics | | | | | |
| Demographic questionnaire | x | | x | x | x |
| Brief Antidepressant Questionnaire (BAQ) | x | | x | x | x |
| Intent to Complete | x | | | | |
| Depression Severity and Anhedonia | | | | | |
| Montgomery Åsberg Depression Rating Scale (MADRS) | x | | x | x | x |
| Hamilton Depression Severity Scale (HAMD) | x | | x | x | x |
| The Dimensional Anhedonia Rating Scale (DARS) | x | | x | x | x |
| Behavioral Activation and Reward Measures | | | | | |
| Behavioral Activation for Depression (BADS) | x | | x | x | x |
| Anticipatory and Consummatory Interpersonal Pleasure Scale (ACIP) | x | | x | x | x |
| Clinical Characteristics | x | | | | |
| Mini-Mental State Examination (MMSE) | x | | | | |
| Interpersonal Problems Inventory – 32 items (IIP-32) | x | | | | x |
| Duke Social Support Index | x | | x | x | x |
| Revised UCLA Loneliness scale | x | | | | x |
| Treatment Rationale Scale | | x | | | |
| MRI tasks | x | | | x | x |
| Probabilistic Reversal Learning task | x | | | x | x |
| Social Incentive Delay task | x | | | x | x |
| Adverse Event Evaluation | | x----- | | | x |

Trained research assistants unaware of study hypotheses will collect weekly clinical and self-report ratings at each study time point via zoom, and in person assessments will be offered if needed.

- **Demographics:** Our demographics questionnaire includes age, gender, race, religion, living conditions, marital status, occupation, birth place, and education.

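### The SH models admit baseline social support only if the arms happen to differ on it, a criterion that does not address confounding within the Engage & Connect arm

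*Combined protocol and SAP*

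**What the plan says.** Sections 3.1 and 12.1 state SH as a within-arm claim: among Engage & Connect participants, change in rsFC (SH1a) and in BADS (SH1b) will predict later MADRS reduction, and this will not be seen under SRP. The pattern is to be read as evidence of the therapy's mechanism. Five models are planned, four for the PVS regions and one for BADS, with Holm adjustment over the five.

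The covariate rule appears in 12.1 and again in 12.4.2: "We will include fixed effects for age, gender, antidepressant use, or any other variable that will be unbalanced between the groups". No threshold for imbalance is given, and social support is not named anywhere in section 12.

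The background gives social support a prominent place. Section 2.2 reports that "high perceived social support predicts early response to psychotherapy". Section 2.3, repeated in 3.2, says the study rests on modelling that "identified perceived social support as the strongest predictor of early response to psychotherapy". The therapy is described in 2.2 as one "whose principal intervention is exposure to meaningful, rewarding social activities with significant others". The "Duke Social Support Index" is scheduled in 6.1 at baseline and at Weeks 3, 5 and 9. Section 6.1 says that it covers subjective and instrumental support and the amount of social interaction.

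**The concern.** SH relates one post-baseline change to a later outcome. Randomisation protects the comparison of arms but not this association, so anything that drives both changes can create it. A variable can be perfectly balanced between arms and still confound fully within one of them. The imbalance rule therefore selects covariates on the wrong ground for SH.

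Social support is the obvious candidate. People with more support have more opportunity for the social activities that the therapy assigns, and may also improve more for other reasons. If so, an association between BADS gain and MADRS fall could arise without BADS change doing any work, and would be read as the mechanism of the therapy.

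The expected absence of the association under SRP is only partial protection. SRP assigns no social activities, so support that acts by enabling those activities could produce the same contrast between arms. No arm-by-predictor interaction test is specified. A random intercept, stated only for H1 to H3, would not help either, because it is assumed independent of the predictors.

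**Working it through.** **The plan's own figure.** There is none to reproduce. The text headed Power Analysis in 12.1 lists outcomes and time points but gives no effect size, SD, correlation or power.

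**Inputs from the documents.** 30 participants per arm (1.1, 3.1). Attrition about 10% (4.1, 7.12), so 30 × 0.9 = 27 per arm. Overall Type I error 5% with Holm over five SH tests (12.4.2), so the first step is 0.05/5 = 0.01.

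**Assumptions.** Tests are two-sided (the plan does not say). The true effect of predictor change on MADRS is zero. Baseline support has correlation a with predictor change and −b with the MADRS outcome. The documents give neither, so a range is shown. The repeated-measures model is reduced to one correlation test without the other covariates, so the figures are illustrative.

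**Step 1: spurious correlation.** With support as the only common cause, r = −a × b.

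**Step 2: false-positive rate without support.** By Fisher's transformation, δ = atanh(|r|) × √(n − 3), with √24 = 4.899. The rejection probability is Φ(δ − c) + Φ(−δ − c), with c = 1.960 at 5% and 2.576 at 1%. Example for |r| = 0.12: δ = 0.1206 × 4.899 = 0.591, giving Φ(−1.369) + Φ(−2.551) = 0.0855 + 0.0054 = 9.1%. Simulation agrees:

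| a / b | r | at 5% | at 1% (first Holm step) |
|---|---|---|---|
| 0.2 / 0.3 | −0.06 | about 6% | 1.4% (1.3% by the formula) |
| 0.3 / 0.4 | −0.12 | about 9% | 2.4% |
| 0.4 / 0.5 | −0.20 | about 17% | 5.6% |

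**Step 3: with support in the model.** The simulated rates return to about 5% and 1% in all three cases.

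**Step 4: does more data help?** No. With both correlations at 0.4, the unadjusted rate at the 5% level is 12.4% for n = 27 and 21% for n = 54, because r stays the same while the test becomes more sensitive.

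**Step 5: how often would the imbalance rule admit support?** Under randomisation with 30 per arm, the standardised difference has SE √(2/30) = 0.258. A trigger of 0.25 is met with probability 2 × [1 − Φ(0.25/0.258)] = 33%; a trigger of 0.5, about 5%; a trigger of p < 0.05, 5%. Which of these applies is not stated.

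**Step 6: precision.** Adding support cuts the outcome's residual variance, but it also removes part of the predictor's variance. In large samples the SE ratio is √{(1 − b²) / [(1 − a²)(1 − a²b²)]}. At a = 0.3, b = 0.4 this is √[0.84 / (0.91 × 0.9856)] = 0.968. In simulation with n = 27 the mean SE changes as follows:

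| a / b | change in SE |
|---|---|
| 0.2 / 0.3 | −0.4% |
| 0.3 / 0.4 | about −1% |
| 0.4 / 0.5 | −1.6% |
| 0.4 / 0.4 | about +3% |

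Taking √(1 − 0.16) = 0.917 as an 8% gain would be right only if support were unrelated to the predictor, in which case there would be no confounding.

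**The case against.** The best counter-argument is that only half of the confounding path is documented. The background ties perceived support to early response, but nothing ties baseline support to BADS change. The nearest statement, "Activities involving social interactions with significant others (but not solitary activities) predicted subsequent increase in behavioral activation and reduction of depression", concerns activities carried out during therapy, which are the intervention and not a baseline trait. The cited finding is also about early response, whereas SH concerns subsequent reduction. This stands: the common-cause argument is plausible, not shown.

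It stands more strongly for SH1a, since no text links support to rsFC change. A reader might infer that all five models are equally exposed; the documents do not support that.

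The cited predictor is perceived support, while the Duke index is broader. That is a fair point and bears on which score to use.

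Loneliness, interpersonal problems, anhedonia, expectancy and alliance are measured too, and 27 participants cannot carry every candidate. That argues for restraint. But support is the one variable that the protocol itself singles out as the strongest predictor.

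Finally, 1.2.3 lists this objective as exploratory, in a pilot. That limits the consequence but does not make imbalance the right criterion; 12.1 also calls SH the secondary hypothesis and gives it a mechanistic reading.

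**Conclusion.** The concern holds as a limited one. The rule for choosing SH covariates uses between-arm imbalance, which is the wrong test for a non-randomised association within one arm. As a result, the predictor that the protocol calls strongest, and already collects at baseline, is left to chance.

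The size of the bias is unknown. Under the assumed correlations the inflation at the first Holm step is slight in the low and middle cases and reaches 5.6% against 1% only in the highest. Holm's procedure controls multiplicity, not confounding.

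Three stronger readings are tempting and should be resisted:
- The plan does not exclude social support; the imbalance clause could admit it.
- Nothing shows that an SH finding would be spurious.
- Adjustment should not be promoted as a gain in precision: the SE changes by roughly −2% to +3%.

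The case is strongest for SH1b. The primary hypothesis H1, and H2 and H3, are not touched.

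**What to change.** In 12.1 and 12.4.2:
- Prespecify the baseline Duke Social Support Index as a fixed covariate in the SH1b (BADS) model, whatever the balance between arms. Prefer its subjective-support part, which is closest to the perceived support cited in the background, and name the score used.
- Use the baseline value only. Week 3, 5 and 9 values may lie on the pathway from therapy to outcome.
- Report the SH1b model without this covariate as a sensitivity analysis.
- Add the same covariate to the four rsFC models as a sensitivity analysis, not as the main model.

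The cost is one degree of freedom in a model with about 27 participants, a few lines of SAP text and slightly more analysis work. No new data are needed.

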1.1 Schema

*The time point(s) indicated in the schematic should correspond to the time point(s) in **Section 6.1, Schedule of Assessments**, e.g., Visit 1; Visit 2; etc.*

Note. 60 patients will be randomly assigned to 9-weeks of either “Engage & Connect” (N=30) or “SRP” (N=30); BADS = Behavioral Activation for Depression scale; MADRS = Montgomery-Asberg Depression Rating Scale; rsFC = resting state functional connectivity; PHQ9 = Patient Health Questionnaire; SID Task = Social Incentive Delay Task

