Patient adherence to intervention (i.e. attendance) will be monitored by the PI and staff: We have developed procedures to minimize risk to our participants, increase retention, and create conditions that make study participation as comfortable as possible. To this end, we will educate participants regarding study procedure and commitment during the informed consent process. We will schedule appointments early in the day or at the participants’ convenience. Our team will call participants prior to each appointment to provide reminders and assist with transportation arrangements. Funds for transportation are included in our budget in order to increase accessibility. The PI or staff member will accompany participants to all MRI scans and be present during scanning sessions in order to maximize comfort and address any questions or concerns that may arise. The PI will collaborate with trained and experienced technicians at our MRI Center to reduce wait time and optimize efficiency of the MRI procedures. The PI will train study personnel in recruitment and data collection procedures with an emphasis on clear communication, sensitivity, and multicultural competence. These measures have led to high retention rates and participant satisfaction in our Institute’s randomized clinical trials. Based on data collected in previous psychotherapy trials at the Institute, we anticipate an attrition rate of ~10%, which has been incorporated into our power analyses.

8. Study Intervention Discontinuation and Participant Discontinuation/Withdrawal

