12.4 Analysis of Endpoints

12.4.1 Analysis of Primary Endpoints

We will implement mixed-effects models using the *lme4* package in R.⁴⁶ For **H1**, **H2**, and **H3** we will include subject-specific random intercept and fixed effects for time-related parameter(s).

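### Selecting extra covariates by between-arm imbalance is the wrong rule for the models relating predictor change to later MADRS (SH), and baseline MADRS is not a named covariate

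*Combined protocol and SAP*

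**What the plan says.** The covariate rule appears in the same words in the Analysis Plan under 12.1 and in 12.4.2: "We will include fixed effects for age, gender, antidepressant use, or any other variable that will be unbalanced between the groups". In 12.4.2 it stands within the description of the SH models. In 12.1 it follows both H1-H3 and SH. Neither section lists candidate variables or says what test or threshold defines imbalance.

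SH is described in 1.2.3 as evaluating, in Engage & Connect participants, whether "change in rsFC of the PVS and behavioral activation (BADS) predicts subsequent reduction in depression severity (MADRS"). Section 12.1 adds of the comparison arm: "These relationships will not be observed in the SRP treated group". The plan does not say whether this contrast comes from separate fits per arm or from a group interaction. The dependent variables are MADRS levels: Weeks 5 and 9 for the four connectivity models, and Weeks 3, 5 and 9 for the BADS model. Baseline MADRS is not named as a covariate.

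For H1-H3, section 12.4.1 says only that "we will include subject-specific random intercept and fixed effects for time-related parameter(s"). It writes no group term and no covariates. On multiplicity the plan says "We will control the overall Type I error rate at 5% using" Holm's procedure, with four comparisons in H1 and five in SH.

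**The concern.** After randomisation, a baseline difference between arms is a chance event. It carries no information about whether the variable predicts outcome. SH also does not estimate a difference between arms: it estimates how a patient's change in connectivity or BADS relates to that patient's later MADRS. A third variable can bias this relation only if it is tied to both sides of it, and balance between arms does not reveal that. This is so whether SH is fitted per arm or with an interaction, because in either case the quantity of interest is a slope across patients within treatment.

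Initial severity is an obvious candidate. The hypothesis concerns reduction in MADRS, but the outcome is the later level, and patients who start higher may both end higher and change differently on the predictor. Under the stated rule, baseline MADRS becomes a covariate only if the arms happen to differ on it.

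At stake is the trial's mechanism claim. A spurious association could be read as evidence that the therapy works through the reward system. Holm's correction covers the number of tests; it does not remove bias from an omitted confounder.

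**Working it through.** The plan states no effect size, SD or covariate correlation, so it has no figure of its own to reproduce. It mentions a power analysis (attrition "which has been incorporated into our power analyses", section 7.12) but gives no numbers from it.

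**Inputs from the plan**
- Section 1.1: "60 patients will be randomly assigned to 9-weeks of either" arm, 30 per arm.
- Section 7.12: "we anticipate an attrition rate of ~10" per cent, hence 30 × 0.9 = 27 completers per arm.
- Section 6.1, baseline variables other than the three named: seven demographic items (race, religion, living conditions, marital status, occupation, birth place, education) and nine scales (MADRS, HAMD, DARS, BADS, ACIP, MMSE, IIP-32, Duke index, UCLA scale). 7 + 9 = 16.

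**Assumptions**
- One confounder correlated r with both the predictor change and later MADRS, with no true association otherwise.
- A single slope in n = 27, tested two-sided at 5%. This simplifies the planned repeated-measures model and takes each test before Holm.
- The 16 variables are independent.

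**Step 1. How often is something flagged by chance?** The probability of at least one flag among k variables is 1 − (1 − α)^k.
- α = 0.05: 1 − 0.95^16 = 1 − 0.440 = 56%.
- α = 0.10: 1 − 0.90^16 = 1 − 0.185 = 81%.

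These are upper bounds if the variables are positively correlated.

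**Step 2. How much depends on the unstated threshold?** A given variable enters 5% of the time under p<0.05 and 20% under p<0.20. At 30 per arm its standardised difference exceeds 0.25 with probability 34% and 0.1 with probability 70%. Of 16 variables, the expected number entering therefore runs from 16 × 0.05 = 0.8 to 16 × 0.70 = 11.2.

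**Step 3. Error in SH without adjustment.** The confounder alone induces a correlation ρ = r × r between predictor and outcome. By Fisher's transformation the test statistic has mean δ = atanh(ρ) × √(27 − 3), and the rejection rate is P(Z > 1.96 − δ) + P(Z < −1.96 − δ).
- r = 0.3: ρ = 0.09, δ = 0.0902 × 4.899 = 0.442, rate 7.3%.
- r = 0.4: ρ = 0.16, δ = 0.1614 × 4.899 = 0.791, rate 12.4%.
- r = 0.5: ρ = 0.25, δ = 0.2554 × 4.899 = 1.251, rate 24.0%.

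**Step 4. Error under the imbalance rule.** With p<0.05 the confounder enters 5% of the time, so the rate is about 0.95 × (Step 3) + 0.05 × 5%: 7.2%, 12.0% and 23.0%.

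**Step 5. Simulation (10,000 trials per row).**

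| r | never adjusted | p<0.05 rule | p<0.20 rule | always adjusted |
|---|---|---|---|---|
| 0 | 5.2% | 5.2% | 5.2% | 5.0% |
| 0.3 | 7.9% | 7.7% | 7.3% | 5.0% |
| 0.4 | 12.3% | 12.0% | 11.0% | 5.0% |
| 0.5 | 24.6% | 23.7% | 21.0% | 5.1% |

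A second simulation gave 7.0%, 11.6% and 23.2% under the p<0.05 rule at r = 0.3, 0.4 and 0.5. Without adjustment it gave 7.1%, 11.8% and 24.1%, and with prespecified adjustment 4.4-5.0%. A p-value rule thus performs almost like no adjustment. A looser rule helps only because the variable enters more often: with 70% entry at r = 0.5, about 0.30 × 24.6% + 0.70 × 5.1% = 11%.

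**Step 6. H1-H3.** In one simulated complete dataset with a random-intercept model, adding a time-constant covariate left the time slope (−0.297, SE 0.131) and a group-by-time term (0.317, SE 0.261) unchanged.

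**The case against.** The defence has several fair points.

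- **The three named covariates look prespecified.** That is the plainer reading, and on it only the additional variables are data-driven. This is why the count used is 16 and excludes age, gender and antidepressant use. The wording should still be made unambiguous.
- **The harm to SH depends on an assumed r.** This stands. With r = 0 the rule costs nothing, and the documents give no correlations. One can say that SH may remain confounded by severity, not that it is.
- **Per-arm fitting is an inference from the hypothesis.** This also stands. The calculation covers a per-arm slope; the argument about the selection criterion does not depend on that choice.
- **The trial is a pilot and 1.2.3 lists the SH question as exploratory.** True, and it limits the weight of the point.

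A reader might infer more: that choosing covariates by imbalance distorts the standard errors and error rate of the treatment comparison. The documents do not support that. Section 12.4.1 writes no between-arm contrast for H1-H3, and Step 6 shows no effect of main-effect covariates on the time slopes with complete data. If a between-arm test were run (27 per arm, 5 or 10 covariates assumed to explain 30% or 50% of outcome variance), a fixed imbalance rule would be conservative, with type I error of 2.6-4.2%. Inflation, to 6.1-7.1%, arises only if the analyst picks the best of four rules after seeing results, and the plan proposes no such search.

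**Conclusion.** The point holds for SH. The plan states a selection rule that does not identify confounders of the relation SH is meant to estimate, leaves its threshold open, and does not name baseline MADRS although the outcomes are MADRS levels. Under a p<0.05 imbalance rule, type I error is about 5% at r = 0, 7-8% at 0.3, 12% at 0.4 and 23-24% at 0.5, against about 5% when the confounder is always included. These figures rest on the assumed r, a single confounder, n = 27 and a simplified one-slope model. Separately, the chance that at least one of 16 other variables is flagged is 56% at p<0.05 and 81% at p<0.10 under independence, so the SH model would depend on chance and on an unstated threshold.

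The conclusion does not extend to the primary analysis: nothing here shows an effect on the H1-H3 time slopes. The wording should be changed before the data are analysed.

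**What to change.** In 12.1 and 12.4.2:

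1. Delete the clause admitting any other unbalanced variable, or move it to a labelled sensitivity analysis with a stated candidate list and threshold.
2. State that age, gender and antidepressant use enter whatever their balance.
3. Add baseline MADRS and the baseline value of the predictor (rsFC or BADS) to each SH model.
4. State whether SH is fitted separately per arm or by a group interaction.
5. Report baseline imbalance descriptively only.

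The cost is SAP wording and one or two degrees of freedom per SH model. All the variables are already collected at baseline, so no visit, measurement or participant is added.
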